4.5.2 Model-based Interim Analysis (Conducted by Study Pharmacologist)

Criterion for opening Arm 2. In addition to the three criteria above, when DTG concentrations from at least 32 evaluable participants (ie, participants in the primary PK analysis population) in Arm 1 are available, a model-based evaluation of DTG PK in these BID participants will occur. The study pharmacologist will develop a nonlinear mixed-effects population pharmacokinetic model, based on available concentrations from all Arm 1 participants (ie, participants in the secondary PK analysis population). From the developed and evaluated model, concentrations for 100 hypothetical participants will be simulated for Arm 2/QD dosing of DTG 1000 times. The parameter of primary interest is C_{24} , the expected DTG concentration at the end of the 24h dosing interval at steady state. For each simulated trial, the 5th, 50th, and 95th percentile of DTG trough concentrations, C_{24} , will be determined.

Of the 1000 simulated trials, the median value of the 5th percentile of DTG C_{24} will be compared to 158 ng/mL, which is the 5th percentile of DTG C_{24} observed for the 10 mg daily DTG dose in SPRING-1. If the median C_{24} value among simulated 5th percentiles is at or above 158 ng/mL, A5372 Arm 2 will open for enrollment, for evaluation of DTG 50 mg QD dosing with 1HP.

4.6 Analysis of the Primary Objective 1 (Conducted by Study Pharmacologist)

In order to determine the dosing for DTG that, when given together with 1HP, achieves target exposures (C_{24}) of standard-dose DTG when it is given without RPT, the distribution of simulated DTG C_{24} values (based on concentrations from Arm 1 and develop population pharmacokinetic model) will be compared

with the historical data from SPRING Study (e.g., C_{tau} in the DTG 10 mg dosing arm) to examine whether dosing of DTG 50 mg BID will maintain above the trough concentration necessary for virologic suppression.

The same analysis will be conducted for Arm 2 if it opens. For this objective, a separate population PK analysis will be conducted (as described in Section 4.5.2).

There is no specific outcome measure associated with this analysis. The “outcome” is the characterization (through modeling) of the relationship between dosing (amounts, frequencies) and CIs around predicted C_{min} values; this analysis will be performed by the study pharmacologist.

4.7 Analysis of Primary Objectives 2 and 3 (outcome measures listed in Section 3.1; conducted by Study Pharmacologist)

For all PK parameters, the following descriptive statistics will be reported by arm and visit: mean, standard deviation, coefficient of variation, median, 5th and 95th percentiles, minimum, and maximum, as well as mean and standard deviation on the natural log (base e) scale. This analysis is conducted using the primary PK analysis population. To assess the overall effect of 1HP on DTG PK parameters, geometric mean ratios (GMRs) and associated 90% CIs will be calculated by arm. The ratio is with (after initiation of 1HP; numerator) vs without (before initiation of 1HP; denominator) co-administered 1HP. The DTG PK parameters are C_{min} , C_{max} , and total daily exposure as measured by AUC_{0-24h} . (For Arm 1, day 28 (BID dosing), participant-specific AUC_{0-24h} will be estimated by combining (summing) areas for the two BID dosing intervals. For Arm 1 day 0, and for Arm 2 days 0 and 28 (QD dosing), participant-specific AUC_{0-24h} values will be estimated from concentrations collected over the single 24-hour dosing interval.)

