10.2.1 Primary Outcome Measures

Evaluation of effect of 1HP on the PK of DTG in plasma

- 10.2.1.1 Plasma DTG PK parameters (C_{max} , area-under-the-curve (AUC₀₋₁₂ for BID & AUC₀₋₂₄ for QD dosing), C_{min}) at Day 0 and Day 28 (-2/+14 days), by arm.
- 10.2.1.2 Plasma DTG PK parameter (C_{trough}) at Day 28 (-2/+14 days), by arm.

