10.6 Analyses

Primary outcome plasma PK parameters (C_{min} , AUC_{0-24h} , and C_{max}) will be determined using **nonlinear mixed-effects population pharmacokinetic modeling**. PK parameters will be log-transformed as needed.

Primary PK analysis:

The bootstrap method with replacement will be applied on the observed C_{trough} values from Arm 1, and the mean and 95% CI of the 5th percentile C_{trough} will be calculated. The **lower bound of a 95% CI around the 5th percentile of C_{min}** from Arm 1 will be compared with the 5th percentile of C_{tau} in the DTG 10 mg dosing arm (i.e., 158 ng/mL) from the SPRING-1 study, which has been demonstrated to be sufficient in maintaining viral suppression. If the **lower bound of the 95% CI around the 5th percentile C_{min}** is greater than 158 ng/mL, the dosing is considered acceptable. The same analysis will be conducted for Arm 2 if it opens.

Geometric mean ratios and associated 90% confidence intervals within arm will be calculated to assess the overall effect of 1HP on DTG PK.

For all PK parameters (including both primary and other outcome PK measures), descriptive statistics including mean, standard deviation, median, interquartile range, minimum, and maximum will be presented. All statistical tests will be performed without adjustment for multiple comparisons unless otherwise stated.

Detailed analysis methods will be put in a Statistical Analysis Plan.

Because PK variability has been associated with differences in drug response, understanding whether differences in DTG and RPT concentrations observed in A5372 have a genetic basis will be explored as an exploratory objective. Polymorphisms in host genes involved in both DTG and RPT metabolism or transport will be explored. The primary genes of interest will include: CYP3A4/5, UGT1A1, PXR (pregnane x receptor), CAR (constitutive androstane receptor), as well as other metabolic enzymes and transporters that may play a role in either DTG or RPT disposition (TBD).

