3.1 Primary Outcome Measures

The primary outcome measures are participant-specific estimates of the day 0 and day 28 plasma DTG PK parameters C_{max} , C_{min} , and area under the concentration-time curve over 24 hours (AUC_{0-24h}) while on the Arm 1 regimen and, if Arm 2 opens, the Arm 2 regimen. [Outcome Measure 10.2.1.1].

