4.8.2 Second and Third Primary Estimands

Objectives 2 and 3 will use the same estimand. The principal stratum strategy is applied for the handling of intercurrent events in the primary analysis of this estimand. This strategy aligns with the definition of participant evaluability as specified in the protocol, and also agrees with the European Medicines Agency bioequivalence guideline, as interpreted in Ring and Wolfsegger (2020). (Bioequivalence is a way to assess drug-drug interactions.) The primary inference approach is estimation of geometric mean ratios, and associated 90% CIs, based on within-subject pairs of PK parameters, where the numerator condition is BID DTG dosed with 1HP, and the denominator condition is QD DTG without TB agents.

Primary Objective 2: To estimate the steady state plasma pharmacokinetics (PK) of DTG when DTG 50 mg is dosed twice daily (BID) with 1HP.	
Primary Objective 3 (Addressed only if Arm 2 opens): To estimate the steady state plasma PK parameters of DTG when DTG 50 mg is dosed once daily (QD) with 1HP.	
Estimand description	Geometric mean ratio of steady state Cmax, Cmin, and AUC _{0-24h} of DTG taken as prescribed before and after completing the TB regimen 1HP in PWH with LTBI
Treatment	
Arm 1
 
 DTG 50 mg orally BID (~12 hours apart) 
 1st dose: DTG 50 mg each morning from non-study ARV supply 2nd dose: DTG 50 mg each evening from study supply 1HP: INH 300 mg + RPT 600 mg orally each morning for 4 weeks 
Arm 2 (upon opening; contingent on assessment of DTG PK data from participants in Arm 1)
 
 DTG 50 mg orally each morning from non-study ARV supply 1HP: INH 300 mg + RPT 600 mg orally each morning for 4 weeks
Target population	Analysis set
PWH with LTBI taking DTG as prescribed and completing 28 doses of 1HP within 6 weeks	The primary PK analysis population (defined above in Section 4.2.1).
Variables	Outcome measure(s)
Steady-state (after 28 days) plasma DTG PK parameters: 
 C_{max}, C_{min}, Area under the concentration-time curve (AUC₀₋₂₄). 	Participant-specific estimates of the day 0 and day 28 steady-state plasma DTG PK parameters C _{max} , C _{min} , and area under the concentration-time curve (AUC _{0-24h}).
Handling of intercurrent events	Handling of missing data

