5.8 Primary Analysis Results

- Descriptive summary of DTG PK parameters (C_{\max} , AUC_{0-24h} , and C_{\min}) at each of the two PK intensive time points, by arm. (Primary analysis population.)
- Geometric mean ratios of DTG PK parameters (C_{\max} , AUC_{0-24h} , C_{\min}), day 28 relative to day 0, and associated 90% CIs, by arm. (Primary analysis population.)

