6.3 Geometric Mean Ratio (GMR) and Associated CI

In assessing drug-drug interactions, pharmacologists and clinicians often characterize the effect of co-administered drug(s) (inhibitor or inducer; “perpetrator”) on the PK parameter of another, target, drug (substrate; “victim”) as the ratio of a PK parameter when measured under 2 different conditions.

Generally, the *numerator* of the ratio represents PK parameter of the target drug *when taken with the co-administered drug(s)*, and the *denominator* represents the target drug PK parameter when the target drug

is taken alone. Estimates near 100% indicate co-administered drug has no effect; estimates significantly below 100% indicate that the co-administered drug up-regulates the metabolism of target drug thereby decreasing systemic exposure to the target drug; and estimates significantly above 100% indicate that the co-administered drug down-regulates the metabolism of target drug thereby increasing exposure.

The geometric mean ratio (GMR) is used to estimate the effects of the interacting drug, with the corresponding CI providing inference. To estimate the ratio on the original scale, the sample mean and standard deviation on the log scale are used, along with the logarithmic identity $\log\left(\frac{B}{A}\right) = \log(B) - \log(A)$ [4].

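### In Arm 1 the primary GMR compares DTG 50 mg BID + 1HP with 50 mg QD alone, but the plan labels and reads it as the effect of 1HP

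*SAP*

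**What the plan says.** - **Label.** SAP 4.7 gives the purpose of the ratio: "To assess the overall effect of 1HP on DTG PK parameters, geometric mean ratios (GMRs) and associated 90% CIs will be calculated by arm". Protocol 10.6 says the same: "Geometric mean ratios and associated 90% confidence intervals within arm will be calculated to assess the overall effect of 1HP on DTG PK". SAP 4.7 defines the ratio only as with over without 1HP, and SAP 5.8 reports it as "day 28 relative to day 0, and associated 90% CIs, by arm". Neither mentions the DTG dose.
- **Actual contrast.** SAP 2.1 puts the Day 0 profile on once-daily DTG and the Arm 1 Day 28 profile on twice-daily DTG. SAP 4.8.2 states that "the numerator condition is BID DTG dosed with 1HP, and the denominator condition is QD DTG without TB agents". That sentence covers Objectives 2 and 3 together, although in Arm 2 the numerator is QD DTG with 1HP.
- **AUC.** SAP 4.7 adds the two BID intervals to form the Arm 1 Day 28 AUC0-24. SAP 3.1 defines the outcome as "area under the concentration-time curve over 24 hours (AUC_{0-24h}) while on the Arm 1 regimen", and protocol 10.6 also uses AUC0-24. Protocol 10.2.1.1 instead gives AUC0-12 "for BID & AUC₀₋₂₄ for QD dosing".
- **Reading.** SAP 6.3 says "Estimates near 100% indicate co-administered drug has no effect" and that "estimates significantly above 100% indicate that the co-administered drug down-regulates the metabolism of target drug thereby increasing exposure". It makes no exception for Arm 1, and SAP 6.4 uses the parameters without dose normalisation.
- **Status.** SAP 4.8.2 makes the GMR with its 90% CI the primary inference for Objectives 2 and 3, and plans no sensitivity or supplementary analyses.

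**The concern.** A ratio shows the effect of a co-administered drug only if the target drug is dosed alike in numerator and denominator. That holds in Arm 2. In Arm 1, the second daily DTG dose raises exposure while rifapentine is expected to lower it, so the two changes offset each other in one number. A real loss of exposure can then appear as no effect or as a gain.

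What is at stake is how the primary result is reported. A reader who takes the label in SAP 4.7 and the interpretation in SAP 6.3 at face value would report the wrong size of interaction from the Arm 1 AUC ratio and, for losses below 50%, the wrong direction. The two arms' ratios would also share a label while measuring different things.

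**Working it through.** The plan gives no expected GMR, so there is no figure to reproduce. The check applies the plan's own assumed interaction to the ratio it defines.

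**Inputs from the documents**
- Fall in DTG bioavailability with rifapentine, d: 30% to 50% (protocol 10.4, SAP 2.4).
- Daily DTG dose in Arm 1: 50 mg on Day 0, 100 mg on Day 28.
- Evaluable participants: 32. CI level for GMRs: 90% (SAP 4.3).

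**Assumptions not in the documents**
- Dose-proportional kinetics.
- SD of paired log differences, s: 0.25 to 0.57.
- For C_max and C_min, a one-compartment model with half-life 8 to 16 h and absorption rate 0.5 to 2 per hour.

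**AUC0-24.** At steady state AUC0-24 is proportional to daily dose × F / CL. So the Arm 1 ratio is (100/50) × (1 − d) = 2(1 − d), and the dose-matched ratio is 1 − d.

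| Fall in F | Arm 1 ratio as planned | Dose-matched ratio | Reading of the Arm 1 ratio under SAP 6.3 |
|---|---|---|---|
| 0% | 2.00 | 1.00 | exposure increased |
| 30% | 1.40 | 0.70 | exposure increased |
| 40% | 1.20 | 0.60 | exposure increased |
| 50% | 1.00 | 0.50 | no effect |

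The ratio crosses 1 at d = 50%. Beyond that the direction is right and only the size is wrong.

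**Confidence interval.** The limits are exp(ln GMR ± 1.696 × s/√32). For a 40% fall (GMR 1.20):
- s = 0.25: 1.11 to 1.29
- s = 0.40: 1.06 to 1.35
- s = 0.57: 1.01 to 1.42

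All three exclude 1. Nearer to a 50% fall the interval can include 1: at 45% (GMR 1.10) with s = 0.40 it is 0.98 to 1.24, which reads as no clear effect.

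**C_max and C_min.** These compare 50 mg every 12 h with F = 1 − d against 50 mg every 24 h with F = 1, over the assumed half-life and absorption range.

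| Fall in F | C_max ratio | C_min ratio |
|---|---|---|
| 30% | 0.96 to 1.17 | 1.87 to 2.68 |
| 40% | 0.82 to 1.00 | 1.61 to 2.30 |
| 50% | 0.69 to 0.83 | 1.34 to 1.91 |

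Both are confounded by the regimen change, but not by a fixed factor of 2, so halving does not repair them. If exposure is halved through doubled clearance instead, the ranges are 0.86 to 0.95 (C_max) and 1.02 to 1.24 (C_min).

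**Sensitivity to proportionality.** Protocol 2.1.1 gives SPRING-1 geometric mean troughs of 0.3 and 1.2 ug/mL at 10 and 50 mg, a fourfold rise for a fivefold dose. The exponent is ln 4 / ln 5 = 0.861, so doubling the dose multiplies exposure by 2^0.861 = 1.82. Carried over to AUC, falls of 30%, 40% and 50% give 1.27, 1.09 and 0.91. At 40% the interval then includes 1 for s = 0.40 (0.97 to 1.23), and at 50% the direction is right. All three ratios remain far from 0.70, 0.60 and 0.50.

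**A parallel in the protocol.** Section 2.1.1 reports DTG 100 mg QD with rifampin over 50 mg alone: C_max 1.09 and AUC 0.74. Per unit dose these are 1.09/2 = 0.55 and 0.74/2 = 0.37. It is a single 100 mg dose, not 50 mg twice daily, but it shows how far an unmatched ratio can lie from the dose-matched one.

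**AUC interval.** At steady state, and if the two intervals are alike, BID AUC0-12 over QD AUC0-24 is already a per-dose ratio. Using AUC0-12 (protocol 10.2.1.1) or AUC0-24 (protocol 10.6, SAP 3.1 and 4.7) therefore changes the Arm 1 result about twofold.

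**The case against.** The strongest reply is that the comparison is disclosed and is the useful one. SAP 4.8.2 names both conditions and lists the doses, and SAP 4.7 describes the AUC as total daily exposure. Objectives 2 and 3 ask for DTG kinetics under each regimen, and Objective 1 asks which dosing with 1HP matches standard-dose exposure; an unadjusted regimen ratio helps answer that. This stands, and the calculation itself is not at fault. But disclosure in one section does not correct the label in SAP 4.7 and protocol 10.6.

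Second, SAP 6.3 can be taken as general background that drives no decision. It does hedge with the word Generally, but the hedge concerns how numerator and denominator are defined. It is also the only guidance in the SAP on what a high or low ratio means.

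Third, the interaction is to be quantified elsewhere: protocol 1.4.3 and 10.2.3.4 plan a joint rifapentine-DTG model, and the population model can estimate the bioavailability effect. This narrows the gap. The joint model is exploratory and left to later analysis plans, however, and this SAP does not name any model estimate as the reported 1HP effect.

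Fourth, no information is lost for AUC, since halving the ratio and its limits gives the dose-matched values (1.11 to 1.29 becomes 0.56 to 0.65). That is true under proportionality, and it shows how cheap the correction is. It does not work for C_max or C_min.

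**Conclusion.** The concern holds. The Arm 1 ratio is a regimen comparison, mislabelled as the effect of 1HP and paired with an interpretation that suits only equal-dose contrasts. Over the plan's assumed 30% to 50% fall in bioavailability, the AUC0-24 ratio would be 1.40 to 1.00 where the dose-matched effect is 0.70 to 0.50. This rests on dose-proportionality; with an exponent of 0.86 the planned ratios are 1.27 to 0.91, still far from the dose-matched values. The interval widths rest on an assumed paired SD, and the C_max and C_min ranges on an assumed one-compartment model.

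The consequence is confined to interpretation. Neither opening Arm 2 nor judging a dose acceptable uses the GMR. Because the GMR is the SAP's primary inference for Objectives 2 and 3, the wording should still be corrected before the results are reported. The AUC0-12 versus AUC0-24 conflict, already present within the protocol, needs settling at the same time.

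**What to change.** 1. In SAP 4.7, 4.8.2 and 5.8, label the unadjusted Arm 1 AUC0-24, C_max and C_min ratios as BID + 1HP versus QD alone (regimen comparison). Align the wording of protocol 10.6.
2. As the Arm 1 estimate of the 1HP effect, add either a dose-normalised AUC ratio (Day 28 AUC0-24 divided by 2, or AUC0-12, over Day 0 AUC0-24) or the model-based effect on bioavailability. State the dose-proportionality assumption.
3. Limit the interpretation in SAP 6.3 to dose-matched ratios: Arm 2 and dose-normalised Arm 1.
4. In SAP 4.8.2, state the Arm 2 numerator separately as QD DTG with 1HP.
5. Reconcile AUC0-12 for BID in protocol 10.2.1.1 with AUC0-24 in protocol 10.6 and SAP 3.1 and 4.7.

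The cost is SAP wording, one extra table row from data already collected, and one protocol clarification of the AUC interval.

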4.8 Primary Estimands

The CBAR requirement of defining estimands was enacted after the protocol had been finalized. As a “grandfather clause” compromise, we are only defining estimands for primary objectives with analyses lead by statisticians.

4.8.1 First Primary Estimand

This objective will be addressed by the pharmacologist; the corresponding estimand is not defined in this analysis plan.

4.8.2 Second and Third Primary Estimands

Objectives 2 and 3 will use the same estimand. The principal stratum strategy is applied for the handling of intercurrent events in the primary analysis of this estimand. This strategy aligns with the definition of participant evaluability as specified in the protocol, and also agrees with the European Medicines Agency bioequivalence guideline, as interpreted in Ring and Wolfsegger (2020). (Bioequivalence is a way to assess drug-drug interactions.) The primary inference approach is estimation of geometric mean ratios, and associated 90% CIs, based on within-subject pairs of PK parameters, where the numerator condition is BID DTG dosed with 1HP, and the denominator condition is QD DTG without TB agents.

Primary Objective 2: To estimate the steady state plasma pharmacokinetics (PK) of DTG when DTG 50 mg is dosed twice daily (BID) with 1HP.	
Primary Objective 3 (Addressed only if Arm 2 opens): To estimate the steady state plasma PK parameters of DTG when DTG 50 mg is dosed once daily (QD) with 1HP.	
Estimand description	Geometric mean ratio of steady state Cmax, Cmin, and AUC _{0-24h} of DTG taken as prescribed before and after completing the TB regimen 1HP in PWH with LTBI
Treatment	
Arm 1
 
 DTG 50 mg orally BID (~12 hours apart) 
 1st dose: DTG 50 mg each morning from non-study ARV supply 2nd dose: DTG 50 mg each evening from study supply 1HP: INH 300 mg + RPT 600 mg orally each morning for 4 weeks 
Arm 2 (upon opening; contingent on assessment of DTG PK data from participants in Arm 1)
 
 DTG 50 mg orally each morning from non-study ARV supply 1HP: INH 300 mg + RPT 600 mg orally each morning for 4 weeks
Target population	Analysis set
PWH with LTBI taking DTG as prescribed and completing 28 doses of 1HP within 6 weeks	The primary PK analysis population (defined above in Section 4.2.1).
Variables	Outcome measure(s)
Steady-state (after 28 days) plasma DTG PK parameters: 
 C_{max}, C_{min}, Area under the concentration-time curve (AUC₀₋₂₄). 	Participant-specific estimates of the day 0 and day 28 steady-state plasma DTG PK parameters C _{max} , C _{min} , and area under the concentration-time curve (AUC _{0-24h}).
Handling of intercurrent events	Handling of missing data

IE: Failure to take DTG as prescribed (1) for 3 days prior to starting 1HP (Principal Stratum strategy)
 
IE: Failure to take DTG (1) and 1HP (2) as prescribed prior to steady state (Principal Stratum strategy)
 
(1) 6 BID 50 mg doses (Arm 1) or 3 QD 50 mg doses (Arm 2)
 
(2) 3 QD doses of 300 INH mg and 3 doses of 600 mg QD doses of RPT
 
For both intercurrent events the Principal Stratum is defined as having taken DTG and 1HP treatment as prescribed
	
Missing data may occur because of:
 
 Failure to appear at study visit (Day 0 or Day 28) Incomplete sampling (≥ 6 timepoints including both 23- and 24-hour samples) Incomplete/unevaluable concentrations when sampled (≥ 6 timepoints including both 23- and 24-hour samples) 
Missing samples and PK concentrations for participants otherwise meeting the dosing criteria will be assumed missing completely at random and participants excluded from the analysis.

Population-level summary measure	Analysis approach
Geometric mean ratio of DTG Cmax, Cmin, and AUC _{0-24h} with (after initiating 1HP; numerator) and without (prior to initiating 1HP; denominator) 1HP	Geometric mean ratio with associated 90% CIs. See Section 8 for details.

Sensitivity Analyses

No sensitivity analyses are planned.

Supplementary analyses

No supplementary analyses are planned.

4.9 Analysis Addressing the Safety, Tolerability and Virologic Suppression Secondary Objectives (Conducted by Statisticians)

For the Safety Analysis Population (see Section 4.2.3), proportions of the events listed in **Section 3.2** will be reported by arm: (a) the proportion of participants with Grade 3 or 4 AE during administration of DTG with 1HP; (b) the proportion of participants who discontinue study or study drugs during administration of DTG with 1HP; and (c) the proportion of participants with HIV-1 RNA levels >50 copies/mL at the second intensive PK measure and/or at the Follow Up visit. Proportions will be reported along with 95% exact Clopper-Pearson CIs around the proportions.

5 Report components

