1.3 Secondary Objectives

- 1.3.1 To evaluate the safety of coadministration of DTG based ART with 1HP.
- 1.3.2 To evaluate the tolerability of coadministration of DTG based ART with 1HP.
- 1.3.3 To estimate the proportion of participants who maintain virologic suppression when DTG based ART is coadministered with 1HP.

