6.2.4 Discontinuation Evaluations

Evaluations for Participants Who Do Not Start Study Treatment

All eCRFs must be keyed for the period up to and including the entry visit.

Discontinuation Evaluations

If a confirmation of suspected virologic failure visit is not necessary (i.e., plasma HIV RNA is determined to be <50 copies/mL at Day 42), participants should discontinue study once they complete their Day 42 follow-up visit. Refer to the Discontinuation Log in the A5372 eCRF completion guideline.

If a confirmation of suspected virologic failure visit is necessary based on the Day 42 follow-up visit plasma HIV RNA, participants should discontinue study after they complete their Day 49 Confirmation of Suspected Virologic Failure visit. Refer to the Discontinuation Log in the A5372 eCRF completion guideline.

Premature Discontinuation Evaluations

Participants who prematurely discontinue the study will have evaluations performed as indicated in the schedule of evaluations and then be taken off study.

Participants who discontinue study participation due to Grade 3 or 4 toxicity attributed to study drug should have premature study discontinuation evaluations completed per the SOE when the toxicity has decreased to Grade ≤2 and then be taken off study. No further evaluations can be performed on a participant after study discontinuation. Refer to the Discontinuation Log in the A5372 eCRF completion guideline.

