4.2.3 Safety Analysis Population

Safety Analysis Population: The Safety Analysis Population consist of all participants who have taken at least one dose of RPT, at least one dose of INH, and at least 2 doses of DTG (Arm 1) or at least 1 dose of DTG (Arm 2).

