5.9 Secondary Analysis Results (Safety, Tolerability, Day 28 Viral Load)

- Summary of all new, post-entry reportable AEs by MedDRA high-level term and grade occurring during administration of DTG with 1HP, by arm. (Safety analysis population)
- Summary of SAEs by MedDRA code, by arm. (Safety analysis population)
- Discontinuation of study drugs during DTG and 1HP dosing, by arm (study drugs to include RPT, INH, DTG and NRTIs). (Safety analysis population)
- Discontinuation of study during DTG and 1HP dosing, by arm. (Safety analysis population)
- HIV-1 RNA levels >50 copies/mL at Day 28 (-2/+14 days) and/or at the Follow Up visit. (Safety analysis population)
- Analyses done for the Safety Analysis Population. Proportion of participants exhibiting each event is reported, along with the associated exact, 95% Clopper-Pearson binomial confidence intervals (CIs). For the AEs, each participant is counted only once, in the highest grade observed for the participant.

6 Calculation of geometric mean ratio and associated confidence interval

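### The SAP reports HIV-1 RNA above 50 copies/mL over everyone dosed, with no rule for missing results; read literally, missing viral loads are grouped with 50 or below

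*SAP*

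**What the plan says.** Secondary Objective 1.3.3 in the protocol is "To estimate the proportion of participants who maintain virologic suppression when DTG based ART is coadministered with 1HP". The matching outcome, Protocol 10.2.2.3, is a value above 50 copies/mL at Day 28 and/or Follow Up.

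SAP 4.9 sets the analysis set for the secondary proportions: "For the Safety Analysis Population (see Section 4.2.3), proportions of the events listed in" SAP Section 3.2. The virologic item is "c) the proportion of participants with HIV-1 RNA levels >50 copies/mL at the second intensive PK measure and/or at the Follow Up visit". SAP 5.9 repeats event and population: "HIV-1 RNA levels >50 copies/mL at Day 28 (-2/+14 days) and/or at the Follow Up visit. (Safety analysis population". On precision, SAP 4.9 says "Proportions will be reported along with 95% exact Clopper-Pearson CIs around the proportions".

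SAP 4.2.3 defines the population by dosing alone. For Arm 1 it is "all participants who have taken at least one dose of RPT, at least one dose of INH, and at least 2 doses of DTG"; Arm 2 requires one DTG dose. A viral load result is not a condition of membership.

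The only missing-data rule in the SAP is in the estimand table for Primary Objectives 2 and 3: "Missing samples and PK concentrations for participants otherwise meeting the dosing criteria will be assumed missing completely at random and participants excluded from the analysis". It concerns PK data. Nothing equivalent exists for viral load.

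**The concern.** The stated population and event together define a proportion. Its numerator needs an observed value above 50, while its denominator needs only doses taken. Someone with no result therefore contributes the same as someone measured at or below 50.

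Missing results are foreseeable, and probably not at random:

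- Protocol 8.1.2 to 8.4 take participants off study after related Grade 3 or 4 toxicity or suspected rifamycin hypersensitivity, once the event has eased. Protocol 8.1.1 does the same when a study-supplied drug is stopped for a milder event.
- Protocol 9.2 lists failure to complete an intensive PK visit as a reason for leaving the study, so a missed Day 28 visit can also remove Follow Up.
- Protocol 6.2.4 adds: "No further evaluations can be performed on a participant after study discontinuation".
- Protocol 10.4 replaces participants who lack the required PK samples. If dosed, they remain in the Safety Analysis Population.

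Under Protocol 8.3 and the suicidal ideation rule in 8.4, locally provided DTG is stopped as well, so suppression cannot be presumed for those participants.

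The and/or wording leaves a second gap: it does not say how to classify a participant with one result at or below 50 and the other missing.

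At stake is the virologic figure that readers will set beside the PK results. Protocol 10.5.1 also has the proportion above 50 reported at the Arm 1 interim review, again without a rule for missing results.

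**Working it through.** **The plan's own figure.** The only stated number that bears on the denominator is 36 enrolled per arm against 32 evaluable (Protocol 10.4, SAP 2.4): 36/32 − 1 = 12.5%, given as about 12%. This reproduces, but it is an allowance for lost PK data. No virologic rate, precision or missing fraction is stated.

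**Inputs.** N = 36 dosed in an arm (planned enrolment). Let m be the number with no result at either visit and x the number with an observed value above 50. The documents give neither; I assume m from 0 to 8 and x from 0 to 2.

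**Three rules.**

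1. Full denominator, the literal reading of SAP 4.9: x/N.
2. Observed only: x/(N − m).
3. Missing counted as not suppressed: (x + m)/N.

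If m covers all the missing results, the complete-data proportion for the same event lies between rules 1 and 3. Rule 2 equals it in expectation only if those without results have the same risk as those with them.

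**Intervals.** Exact Clopper-Pearson for k events in n. The lower limit is the 2.5% quantile of Beta(k, n − k + 1), and the upper limit is the 97.5% quantile of Beta(k + 1, n − k). For k = 0 the lower limit is 0 and the upper is 1 − 0.025^(1/n): n = 36 gives 9.7% and n = 32 gives 10.9%.

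**Results, N = 36.**

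| m | x | Full denominator | Observed only | Missing = not suppressed |
|---|---|---|---|---|
| 2 | 1 | 1/36 = 2.8% (0.1–14.5) | 1/34 = 2.9% (0.1–15.3) | 3/36 = 8.3% (1.8–22.5) |
| 4 | 0 | 0/36 = 0% (0–9.7) | 0/32 = 0% (0–10.9) | 4/36 = 11.1% (3.1–26.1) |
| 4 | 1 | 1/36 = 2.8% (0.1–14.5) | 1/32 = 3.1% (0.1–16.2) | 5/36 = 13.9% (4.7–29.5) |
| 8 | 2 | 2/36 = 5.6% (0.7–18.7) | 2/28 = 7.1% (0.9–23.5) | 10/36 = 27.8% (14.2–45.2) |

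With m = 0 the three rules agree. Each missing participant moves rule 3 by 1/36 = 2.8 points. In terms of suppression, the row with m = 4 and x = 0 reads 36/36 = 100% on the full denominator and 32/36 = 88.9% under rule 3.

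**A larger denominator.** Because replaced participants who were dosed still count, N may exceed 36. With N = 40, m = 4 and x = 1 the three figures are 1/40 = 2.5%, 1/36 = 2.8% and 5/40 = 12.5%.

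**The case against.** The SAP nowhere says that a missing result counts as suppressed. A reader might infer that the plan has adopted that rule. It has not; it is silent, and an analyst could report the number with results as the denominator without contradicting any sentence. This stands: the fault is a missing rule whose literal default is unfavourable, not a stated imputation.

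A reader might also infer that participants who stop early have no viral load by design. The documents do not establish this. Protocol 6.2.4 and Section 8 require discontinuation evaluations before a participant leaves, and the Schedule of Evaluations has a column for them. The schedule as available to me does not show the viral load rows, so I cannot say whether an exit sample is drawn. The outcome wording names only Day 28 and Follow Up, so the SAP would still have to say whether an exit sample counts.

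It is tempting to say that the calculation can only overstate suppression. Grouping missing results with non-events does push that way. But the event is any single value above 50, whereas Protocol 6.2.3 treats such a value at Day 42 as suspected failure pending a confirmatory sample. A transient value therefore counts against suppression, and the net error relative to sustained suppression can run either way.

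Three further points stand in part. The large contrast appears only against missing counted as not suppressed, which is a convention and not the correct answer. Discontinuation is reported separately in SAP 4.9, 5.4 and 5.5, so readers can see how many left, though not how many lacked a viral load. The outcome is a descriptive secondary one, and Arm 2 opens on trough concentrations (Protocol 7.4, SAP 4.5.2).

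**Conclusion.** The point holds as an unhandled missing-data problem in a secondary outcome. With a dose-defined denominator and an observed-event numerator, missing viral loads fall by default with results at or below 50. This biases the estimate for Objective 1.3.3 toward suppression if participants who leave early lack these results.

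The size depends on counts that the documents do not give. In the N = 36 scenarios shown, the full denominator differs from observed-only by at most 1.5 points (5.6% against 7.1%). The difference from missing counted as not suppressed is 11.1 points with 4 missing (4/36). The main loss is that a reader of the planned output could not see where in that range the result lies.

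The difference between the entry criterion (below 50) and the outcome (above 50) affects only a value of exactly 50. It is negligible and does not justify departing from Protocol 10.2.2.3.

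**What to change.** In SAP 4.9 and 5.9:

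- Report, by arm and by visit (Day 28 and Follow Up separately), the number in the Safety Analysis Population with a viral load result, and the proportion above 50 copies/mL among them.
- Add a sensitivity estimate on the full Safety Analysis Population that counts those without a result as not suppressed.
- Give Clopper-Pearson 95% intervals for both.
- If the combined and/or outcome is kept, state how a participant with only one of the two results is classified.
- State how any viral load drawn at premature discontinuation is used.
- Keep the protocol's threshold of above 50.

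The cost is SAP wording and one extra table row, with no new data collection. Reported suppression may look slightly less favourable.
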